### 7.4 End of Treatment

Patients should be seen in the clinic or contacted by telephone to determine if any serious or non-serious adverse events have occurred within 28 days ( $\pm$  3 days) of termination of TAS-102 dosing.

Patients will be followed for 28 days after completion of the last course of any therapy for the documentation of adverse events and concomitant medications.

Off-therapy measurements:

- a. Toxicity assessment, interim medical history and physical examination
- b. Laboratory studies:
  - CBC with differential count
  - CMP

## 7.5 **Follow up/Survival**

Patients will be seen in follow-up at least every three months for the first three years after the initiation of therapy, or the date of death, whichever occurs first. Patients who are alive after three years will have follow up every six months for years four and five, then annual follow ups until date of death, or lost to follow up. Those patients who are lost to follow up will have every effort by telephone and mail to contact them for at least one month past their first missed clinic visit, with at least four documented attempts at contact to be made during that time.

Evaluation will consist of an interim medical history and a physical examination. Additional studies, such as labs (CBC and CMP), and any X-rays, or CT, PET/CT, bone scans or MRI scans used in evaluation of response will be repeated as clinically indicated. Other studies, such as, biopsies, will be performed as clinically indicated.

## 8. **CRITERIA FOR DISEASE EVALUATION**

### 8.1 **Definitions**

Evaluable for toxicity. All patients will be evaluable for toxicity from the time of their dose of any of the three drugs in this study.

Evaluable for objective response. Only those patients who have measurable disease present at baseline, have received at least one cycle of therapy, and have had their disease re-evaluated will be considered evaluable for response. These patients will have their response classified according to the definitions stated below. (Note: Patients who exhibit objective disease progression prior to the end of cycle 1 will also be considered evaluable.)

Evaluable Non-Target Disease Response. Patients who have lesions present at baseline that are evaluable but do not meet the definitions of measurable disease, have received at least one cycle of therapy, and have had their disease re-evaluated will be considered evaluable for non-target disease. The response assessment is based on the presence, absence, or unequivocal progression of the lesions.

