## 3. SELECTION OF SUBJECTS

### 3.1 Number of Subjects

This protocol will enroll up to a maximum of 30 subjects.

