*NOTE: Radiation therapy to a symptomatic solitary lesion may be considered on an exceptional case by case basis after consultation with sponsor-investigator. The subject must have clear measurable disease outside the radiated field. Administration of palliative radiation therapy will be considered clinical progression for the purposes of determining PFS.*

Live vaccines within 30 days prior to the first dose of trial treatment and while participating in the trial. Examples of live vaccines include, but are not limited to, the following: measles, mumps, rubella, chicken pox, yellow fever, rabies, BCG, and typhoid (oral) vaccine. Seasonal influenza vaccines for injection are generally killed virus vaccines and are allowed. However, intranasal influenza vaccines (e.g. Flu - Mist®) are live attenuated vaccines, and are not allowed.

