### 6.3 **Replacement of Subjects**

Subjects will be replaced if they have not received any doses of study drug prior to their continuing participation in the protocol for any reason, or if the patient wishes to discontinue participation in the protocol, but is not discontinued for disease progression, toxicity, or any of the reasons listed in section 6.2.

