### **Disease Parameters**

Measurable disease. Measurable lesions are defined as those that can be accurately measured in at least one dimension (longest diameter to be recorded) as  $\geq 20$  mm by chest x-ray or as  $\geq 10$  mm with CT scan, MRI, or calipers by clinical exam. All tumor measurements must be recorded in millimeters (or decimal fractions of centimeters).

Note: Tumor lesions that are situated in a previously irradiated area are considered measurable only if they have demonstrated growth after completion of the radiation therapy.

Malignant lymph nodes. To be considered pathologically enlarged and measurable, a lymph node must be  $\geq 15$  mm in short axis when assessed by CT scan (CT scan slice thickness recommended to be no greater than 5 mm). At baseline and in follow-up, only the short axis will be measured and followed.

Non-measurable disease. All other lesions (or sites of disease), including small lesions (longest diameter  $< 10$  mm or pathological lymph nodes with  $\geq 10$  to  $< 15$  mm short axis), are considered non-measurable disease. Bone lesions, leptomeningeal disease, ascites, pleural/pericardial effusions, lymphangitis cutis/pneumonitis, inflammatory breast disease, and abdominal masses (not followed by CT or MRI), are considered as non-measurable.

Note: Cystic lesions that meet the criteria for radiographically defined simple cysts should not be considered as malignant lesions (neither measurable nor non-measurable) since they are, by definition, simple cysts.

‘Cystic lesions’ thought to represent cystic metastases can be considered as measurable lesions, if they meet the definition of measurability described above. However, if non-cystic lesions are present in the same patient, these are preferred for selection as target lesions.

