#### For Non-Measurable Disease (*i.e.*, Non-Target Disease)

Non-Target Lesions	New Lesions	Overall Response
CR	No	CR
Non-CR/non-PD	No	Non-CR/non-PD*
Not all evaluated	No	not evaluated
Unequivocal PD	Yes or No	PD
Any	Yes	PD

* ‘Non-CR/non-PD’ is preferred over ‘stable disease’ for non-target disease since SD is increasingly used as an endpoint for assessment of efficacy in some trials so to assign this category when no lesions can be measured is not advised
		

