### **11.2 Analysis of Endpoints/Efficacy**

The primary endpoint to this study will be to document the objective rate of response by RECIST Criteria, version 1.1 of the participants in this trial which will be estimated along with exact 95% binomial confidence intervals.

The secondary endpoints of this study will be to determine the rate of development of toxicities, and the reversibility of toxicities of this regimen; the Objective Response Rate (by RECIST Criteria); the Clinical Benefit Rate (objective response + disease stability rate); the median duration of response in months, and the median Overall Survival.

A secondary endpoint of this study will be progression-free survival following TAS-102 therapy. Kaplan-Meier mean estimates and survival curves of progression-free survival rates will be calculated. Secondary endpoints include clinical benefit rate (CR + PR + SD), toxicities and reversibility of toxicities) will also be estimated along with exact 95% binomial confidence intervals.

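### Entry criteria do not require a measurable lesion, although only patients with measurable baseline disease are evaluable for the primary endpoint

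*Combined protocol and SAP*

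**What the plan says.** Section 11.2 sets the primary endpoint: to "document the objective rate of response by RECIST Criteria, version 1.1", with an exact 95% binomial confidence interval. Section 8.1 then limits who is evaluable for objective response: "Only those patients who have measurable disease present at baseline, have received at least one cycle of therapy", and whose disease has been re-evaluated.

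The eligibility lists (synopsis, and sections 3.2 and 3.3) ask for squamous histology, prior treatment, evidence of progression, performance status and laboratory values. None asks for a measurable lesion. Three places come near:

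- Exclusion J requires growth of a target lesion, but only if that lesion was irradiated.
- Section 5.1 says the same of an irradiated indicator lesion.
- Section 5.2 states "The subject must have clear measurable disease outside the radiated field", but as a condition for palliative radiotherapy during the study, not for entry.

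The protocol also provides for patients without measurable disease. Section 8.1 has a separate evaluability category for "Patients who have lesions present at baseline that are evaluable but do not meet the definitions of measurable disease". Under Disease Parameters it lists "Bone lesions, leptomeningeal disease, ascites, pleural/pericardial effusions" among the non-measurable sites, along with small lesions and nodes. Section 8.2 has a response table headed "For Non-Measurable Disease".

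On numbers, section 3.1 says "This protocol will enroll up to a maximum of 30 subjects". Section 11.1 plans a first stage of 14 evaluable subjects and a total of 30 evaluable subjects. Section 6.3 begins "Subjects will be replaced if they have not received any doses of study drug" and adds certain voluntary discontinuations. It does not mention lack of measurable disease.

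**The concern.** The population that may enter and the population that can answer the primary question do not match. A patient whose only disease is, for example, bone lesions and a pleural effusion can meet every entry criterion, because progression can be documented in non-measurable disease. Under section 4, registration works from an eligibility checklist, so a criterion that is not written will not be checked.

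Section 8.1 excludes that patient from the response evaluation. The patient still receives a cytotoxic drug and takes a place under the cap, in a study whose section 11.1 aims to keep the number of exposed subjects small. What is at stake is the number of patients contributing to the primary estimate, and treatment of patients who cannot contribute to it.

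**Working it through.** **Inputs from the documents.** Response rate of interest 20%; stop if 0 of 14 evaluable subjects respond; chance of wrongly stopping at a 20% rate below 5%; 30 evaluable subjects with a standard error of no more than 9% (all section 11.1); cap of 30 enrolled (section 3.1).

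**Assumption.** The documents give no share of patients without measurable disease. I use 3 to 6 of 30 (10% to 20%) for illustration.

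**1. The plan's own figures.**
- False stop: (1 − 0.20)^14 = 0.0440, or 4.4%. This agrees with the stated figure of below 5%.
- Standard error, sqrt(p(1 − p)/n), at p = 0.20 and n = 30: sqrt(0.16/30) = 0.0730, or 7.3%. At p = 0.50 it is sqrt(0.25/30) = 0.0913, which meets 9% only after rounding.

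**2. False stop under section 8.1.** The 14 are evaluable subjects, so a patient without measurable disease is not among them. The calculation is unchanged at 4.4%.

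**3. Precision when the cap of 30 binds.**

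| Without measurable disease (assumed) | Evaluable | SE at p = 0.20 |
|---|---|---|
| 0 | 30 | sqrt(0.16/30) = 7.3% |
| 3 | 27 | sqrt(0.16/27) = 7.7% |
| 6 | 24 | sqrt(0.16/24) = 8.2% |

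At a 20% rate the standard error passes 9% only below 20 evaluable: sqrt(0.16/20) = 8.94% and sqrt(0.16/19) = 9.18%. That would take 11 or more of the 30. If the 9% is read as a worst case at p = 0.50, it becomes sqrt(0.25/27) = 9.6% or sqrt(0.25/24) = 10.2%, but that rate is far from the one of interest.

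**4. Exact 95% interval at an observed 20%.** Clopper–Pearson limits are the 0.025 quantile of Beta(x, n − x + 1) and the 0.975 quantile of Beta(x + 1, n − x).
- 6/30: 7.7% to 38.6%, width 30.9 percentage points.
- 5/25: 6.8% to 40.7%, width 33.9 percentage points. (25 is used because 20% of it is a whole number.)

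**5. If accrual instead ran on to 30 evaluable.** Enrolment needed is 30/(1 − share), rounded up: 30/0.90 = 33.3, so 34; 30/0.80 = 37.5, so 38. Precision is then kept, and the cost becomes 4 to 8 extra patients treated.

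**The case against.** **No stated operating figure fails.** This is correct under section 8.1 at the 20% rate. The plan is one of estimation, with no success threshold after stage 1, so no later decision rule is affected either.

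**The shortfall below 30 belongs to another conflict.** Section 11.1 counts evaluable subjects, so accrual could pass over patients without measurable disease. The number falls short only because section 3.1 caps enrolment at 30. This stands in part. Resolving that conflict in favour of 30 evaluable would remove the loss of precision, but not the treatment of patients who cannot inform the primary endpoint.

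**Admitting these patients may be deliberate.** Sections 8.1 and 8.2 give them a category and a table, and they still contribute to toxicity, progression-free survival and overall survival. That is fair, but nothing in the plan says that treating patients who cannot inform the primary endpoint is intended. The references to target and indicator lesions in exclusion J and section 5.1 suggest that such lesions were expected; they do not require one.

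**A stronger reading is tempting.** Section 11.1 defines evaluability for activity by two cycles and does not mention measurability. A reader might infer that patients without measurable disease enter the 14, can hardly respond, and push the false-stop risk above the stated 5%. The documents do not support this. The sentence adds a two-cycle condition to having been dosed; it does not withdraw the section 8.1 requirement.

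**Conclusion.** The concern holds as a mismatch between eligibility and the primary-endpoint population, and it should be corrected. The omission is certain on the text. Its size is not, because the number of affected patients is assumed.

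With 3 to 6 of 30 affected and the cap binding, precision falls modestly: at most about 0.9 percentage points on the standard error at a 20% rate (8.2% − 7.3%), and about 3 percentage points on the width of the exact interval in the 5/25 example. A reader might infer that the trial's error rate or its 9% precision target is broken. At the 20% rate of interest neither is. The case for the change is that a cheap criterion prevents avoidable exposure and keeps places for patients who count toward the endpoint.

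**What to change.** - Add to section 3.2, the synopsis and the eligibility checklist: *at least one measurable lesion by RECIST 1.1 as defined in Section 8.1*.
- State in section 11.1 that the 14 and the 30 evaluable subjects must meet the measurable-disease requirement of section 8.1.
- Mark the non-target-only category in section 8.1 and the non-measurable-disease table in section 8.2 as not applying to the primary endpoint. This also settles whether a complete response under that table would count.

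The cost is a few lines of text and slightly slower accrual, since patients with only non-measurable disease become ineligible. The population for the primary estimate does not narrow, because section 8.1 already excludes these patients from it.

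This does not settle two separate conflicts, which need their own correction: 30 enrolled (section 3.1) against 30 evaluable (section 11.1), and one cycle (section 8.1) against two (section 11.1) for evaluability.

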### **Disease Parameters**

Measurable disease. Measurable lesions are defined as those that can be accurately measured in at least one dimension (longest diameter to be recorded) as  $\geq 20$  mm by chest x-ray or as  $\geq 10$  mm with CT scan, MRI, or calipers by clinical exam. All tumor measurements must be recorded in millimeters (or decimal fractions of centimeters).

Note: Tumor lesions that are situated in a previously irradiated area are considered measurable only if they have demonstrated growth after completion of the radiation therapy.

Malignant lymph nodes. To be considered pathologically enlarged and measurable, a lymph node must be  $\geq 15$  mm in short axis when assessed by CT scan (CT scan slice thickness recommended to be no greater than 5 mm). At baseline and in follow-up, only the short axis will be measured and followed.

Non-measurable disease. All other lesions (or sites of disease), including small lesions (longest diameter  $< 10$  mm or pathological lymph nodes with  $\geq 10$  to  $< 15$  mm short axis), are considered non-measurable disease. Bone lesions, leptomeningeal disease, ascites, pleural/pericardial effusions, lymphangitis cutis/pneumonitis, inflammatory breast disease, and abdominal masses (not followed by CT or MRI), are considered as non-measurable.

Note: Cystic lesions that meet the criteria for radiographically defined simple cysts should not be considered as malignant lesions (neither measurable nor non-measurable) since they are, by definition, simple cysts.

‘Cystic lesions’ thought to represent cystic metastases can be considered as measurable lesions, if they meet the definition of measurability described above. However, if non-cystic lesions are present in the same patient, these are preferred for selection as target lesions.

Target lesions. All measurable lesions up to a maximum of 2 lesions per organ and 5 lesions in total, representative of all involved organs, should be identified as **target lesions** and recorded and measured at baseline. Target lesions should be selected on the basis of their size (lesions with the longest diameter), be representative of all involved organs, but in addition should be those that lend themselves to reproducible repeated measurements. It may be the case that, on occasion, the largest lesion does not lend itself to reproducible measurement in which circumstance the next largest lesion which can be measured reproducibly should be selected. A sum of the diameters (longest for non-nodal lesions, short axis for nodal lesions) for all target lesions will be calculated and reported as the baseline sum diameters. If lymph nodes are to be included in the sum, then only the short axis is added into the sum. The baseline sum diameters will be used as reference to further characterize any objective tumor regression in the measurable dimension of the disease.

Non-target lesions. All other lesions (or sites of disease) including any measurable lesions over and above the 5 target lesions should be identified as **non-target lesions** and should also be recorded at baseline. Measurements of these lesions are not required, but the presence, absence, or in rare cases unequivocal progression of each should be noted throughout follow-up.

## Methods for Evaluation of Measurable Disease

All measurements should be taken and recorded in metric notation using a ruler or calipers. All baseline evaluations should be performed as closely as possible to the beginning of treatment and never more than 4 weeks before the beginning of the treatment.

The same method of assessment and the same technique should be used to characterize each identified and reported lesion at baseline and during follow-up. Imaging-based evaluation is preferred to evaluation by clinical examination unless the lesion(s) being followed cannot be imaged but are assessable by clinical exam.

Clinical lesions. Clinical lesions will only be considered measurable when they are superficial (*e.g.*, skin nodules and palpable lymph nodes) and  $\geq 10$  mm diameter as assessed using calipers (*e.g.*, skin nodules). In the case of skin lesions, documentation by color photography, including a ruler to estimate the size of the lesion, is recommended.

Chest x-ray. Lesions on chest x-ray are acceptable as measurable lesions when they are clearly defined and surrounded by aerated lung. However, CT is preferable.

Conventional CT and MRI. This guideline has defined measurability of lesions on CT scan based on the assumption that CT slice thickness is 5 mm or less. If CT scans have slice thickness greater than 5 mm, the minimum size for a measurable lesion should be twice the slice thickness. MRI is also acceptable in certain situations (*e.g.* for body scans).

Use of MRI remains a complex issue. MRI has excellent contrast, spatial, and temporal resolution; however, there are many image acquisition variables involved in MRI, which greatly impact image quality, lesion conspicuity, and measurement. Furthermore, the availability of MRI is variable globally. As with CT, if an MRI is performed, the technical specifications of the scanning sequences used should be optimized for the evaluation of the type and site of disease. Furthermore, as with CT, the modality used at follow-up should be the same as was used at baseline and the lesions should be measured/assessed on the same pulse sequence. It is beyond the scope of the RECIST guidelines to prescribe specific MRI pulse sequence parameters for all scanners, body parts, and diseases. Ideally, the same type of scanner should be used and the image acquisition protocol should be followed as closely as possible to prior scans. Body scans should be performed with breath-hold scanning techniques, if possible.

PET-CT. At present, the low dose or attenuation correction CT portion of a combined PET-CT is not always of optimal diagnostic CT quality for use with RECIST measurements. However, if the site can document that the CT performed as part of a PET-CT is of identical diagnostic quality to a diagnostic CT (with IV and oral contrast), then the CT portion of the PET-CT can be used for RECIST measurements and can be used interchangeably with conventional CT in accurately measuring cancer lesions over time. Note, however, that the PET portion of the CT introduces additional data which may bias an investigator if it is not routinely or serially performed.

Ultrasound. Ultrasound is not useful in assessment of lesion size and should not be used as a method of measurement. Ultrasound examinations cannot be reproduced in their entirety for independent review at a later date and, because they are operator dependent, it cannot be guaranteed that the same technique and measurements will be taken from one assessment to the next. If new lesions are identified by ultrasound in the course of the study, confirmation by CT or MRI is advised. If there is concern about radiation exposure at CT, MRI may be used instead of CT in selected instances.

Endoscopy or Laparoscopy. The utilization of these techniques for objective tumor evaluation is not advised. However, such techniques may be useful to confirm complete pathological response when biopsies are obtained or to determine relapse in trials where recurrence following complete response (CR) or surgical resection is an endpoint.

Tumor Markers. Tumor markers alone cannot be used to assess response. There are no validated tumor markers for NSCLC, and none are being evaluated here.

Cytology or Histology. These techniques can be used to differentiate between partial responses (PR) and complete responses (CR) in rare cases (*e.g.*, residual lesions in tumor types, such as germ cell tumors, where known residual benign tumors can remain).

The cytological confirmation of the neoplastic origin of any effusion that appears or worsens during treatment when the measurable tumor has met criteria for response or stable disease is mandatory to differentiate between response or stable disease (an effusion may be a side effect of the treatment) and progressive disease.

FDG-PET. While FDG-PET response assessments need additional study, it is sometimes reasonable to incorporate the use of FDG-PET scanning to complement CT scanning in assessment of progression (particularly possible 'new' disease). New lesions on the basis of FDG-PET imaging can be identified according to the following algorithm:

- a. Negative FDG-PET at baseline, with a positive FDG-PET at follow-up is a sign of PD based on a new lesion.
- b. No FDG-PET at baseline and a positive FDG-PET at follow-up: If the positive FDG-PET at follow-up corresponds to a new site of disease confirmed by CT, this is PD. If the positive FDG-PET at follow-up is not confirmed as a new site of disease on CT, additional follow-up CT scans are needed to determine if there is truly progression occurring at that site (if so, the date of PD will be the date of the initial abnormal FDG-PET scan). If the positive FDG-PET at follow-up corresponds to a pre-existing site of disease on CT that is not progressing on the basis of the anatomic images, this is not PD.
- c. FDG-PET may be used to upgrade a response to a CR in a manner similar to a biopsy in cases where a residual radiographic abnormality is thought to represent fibrosis or scarring. The use of FDG-PET in this circumstance should be prospectively described in the protocol and supported by disease-specific medical literature for the indication. However, it must be acknowledged that both approaches may lead to false positive CR due to limitations of FDG-PET and biopsy resolution/sensitivity.

Note: A 'positive' FDG-PET scan lesion means one which is FDG avid with an uptake greater than twice that of the surrounding tissue on the attenuation corrected image.

